5.2. General Methods

Descriptive statistics for binary variables are the proportion (%) and the numerator (n) and the denominator (N) used in the proportion calculation. The 95% CI for percentage, and for the difference in percentages, may also be presented, where appropriate.

Unless otherwise specified, descriptive statistics for continuous variables are n, mean, median, standard deviation, minimum, and maximum.

5.2.1. Analyses for Binary Endpoints and Count Data

Descriptive statistics for binary variables (eg, proportions) are the percentage (%), the numerator (n) and the denominator (N) used in the percentage calculation, and the 95% CIs where applicable.

The exact 95% CI for binary endpoints for each group will be computed using the F distribution (Clopper-Pearson)² and implemented in SAS PROC FREQ.

The 95% CI for the between-group difference for binary endpoints will be calculated using the Miettinen and Nurminen³ method.

Descriptive statistics for count data are incidence rate, the numerator (number of events observed) and the denominator (total person-years of follow-up) used in the incidence rate calculation, and the 95% CIs where applicable.

The exact 95% CI for incidence rates for each group may be computed using the method of Ulm⁴ based on the link between the chi-square distribution and the Poisson distribution.

5.2.2. Analyses for Continuous Endpoints

5.2.2.1. Geometric Mean Titers

The GMTs will be calculated as the mean of the assay results after making the logarithm transformation and then exponentiating the mean to express results on the original scale. Two-sided 95% CIs will be obtained by taking log transforms of assay results, calculating the 95% CI with reference to Student's t distribution, and then exponentiating the confidence limits.

5.2.2.2. Geometric Mean Fold Rises

GMFRs are defined as ratios of the results after vaccination to the results before vaccination. GMFRs are limited to participants with nonmissing values at both time points.

GMFRs will be calculated as the mean of the difference of logarithmically transformed assay results (later time point minus earlier time point) and exponentiating the mean. The associated 2-sided 95% CIs will be obtained by constructing CIs using Student's

t distribution for the mean difference on the logarithm scale and exponentiating the confidence limits.

5.2.2.3. Geometric Mean Ratios

The GMR will be calculated as the mean of the difference of logarithmically transformed assay results and exponentiating the mean. Two-sided CIs will be obtained by calculating CIs using Student's t distribution for the mean difference of the logarithmically transformed assay results and exponentiating the confidence limits.

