**Table 6. HAI Used to Evaluate the Immune Responses Against Influenza, by Season**

	Visit 1 Vaccination	Visit 3 4-Week Follow-Up Visit	Visit 4 6-Month Follow-Up Visit
2023 Southern Hemisphere Influenza Season			
HAIs CCI [REDACTED]	Yes (Subset of samples c )	Yes (Subset of samples c )	No testing
HAIs CCI [REDACTED]	Yes (Subset of samples d )	Yes (Subset of samples d )	Yes (Subset of samples d )

a. Samples from a randomly selected subset of participants CCI [REDACTED] will be tested at Visit 1 and Visit 3 using HAIs CCI [REDACTED]  
 b. From the subset of participants randomly selected to have samples tested at Visit 1 and Visit 3 using HAIs CCI [REDACTED] a select number of these participants will be tested at Visit 4 using HAIs [REDACTED]  
 c. Samples from a randomly selected subset of participants in the southern hemisphere will be tested at Visit 1 and Visit 3 using HAIs CCI [REDACTED]  
 d. The subset of participants randomly selected to have samples tested using HAIs CCI [REDACTED] at Visit 1 and Visit 3 will also be tested using HAIs CCI [REDACTED] at Visit 1, Visit 3, and Visit 4.

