4. ANALYSIS SETS (POPULATIONS FOR ANALYSIS)

Data for all participants will be assessed to determine if participants meet the criteria for inclusion in each analysis population prior to unblinding and releasing the database, and classifications will be documented per standard operating procedures.

Population	Description
Screened	All participants who sign the ICD.
Randomized	All participants who are assigned a randomization number in the IWRS.
Evaluable immunogenicity (HAI assays CCI [REDACTED])	All participants included in the immunogenicity subset who are eligible, receive the study intervention to which they were randomized, have blood drawn for assay testing within the specified time frame (CCI [REDACTED]), have at least 1 valid and determinate assay result (HAI assays CCI [REDACTED]) at the 4-week postvaccination visit, and have no important protocol deviations.
Evaluable immunogenicity (HAI assays CCI [REDACTED])	All participants included in the immunogenicity subset who are eligible, receive the study intervention to which they were randomized, have blood drawn for assay testing within the specified time frame (CCI [REDACTED]), have at least 1 valid and determinate assay result (HAI assays CCI [REDACTED]) at the 4-week postvaccination visit, and have no important protocol deviations.
mITT immunogenicity (HAI assays CCI [REDACTED])	All randomized participants in the immunogenicity subset who receive the study intervention and have at least 1 valid and determinate assay result (HAI assays CCI [REDACTED]) after vaccination.
mITT immunogenicity (HAI assays CCI [REDACTED])	All randomized participants in the immunogenicity subset who receive the study intervention and have at least 1 valid and determinate assay result (HAI assays CCI [REDACTED]) after vaccination.
Evaluable efficacy	All participants who are eligible, receive the study intervention to which they were randomized, and have no important protocol deviations, with surveillance starting at least 14 days after vaccination.
mITT efficacy	All randomized participants who receive the study intervention.

Population	Description
Safety	All participants who receive the study intervention.
Reactogenicity e-diary safety	All participants who receive the study intervention and have at least 1 day of e-diary data transferred for reactogenicity.

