5.1.3. Multiplicity Adjustment

There are 2 hypothesis tests for the primary efficacy objectives (noninferiority, superiority) in each group (18 through 64 years of age, ≥ 65 years of age).

There are 8 hypothesis tests for the secondary immunogenicity objectives CCI assays, separately, with 2 statistical hypotheses for each of the 4 targeted strains for each age stratum (participants 18 through 64 and ≥ 65 years of age).

Only immunogenicity data collected from the CCI will be used for the immunogenicity noninferiority objectives.

For both age strata (participants 18 through 64 and ≥ 65 years of age), the hypothesis for the primary noninferiority efficacy objective will be tested first, followed by the hypothesis for the primary superiority efficacy objective. The superiority efficacy objective will be tested only after the noninferiority efficacy objective has been achieved. The hypotheses related to the secondary immunogenicity objective (HAI assays CCI) for each age stratum will be tested after both primary efficacy objectives in the respective age stratum have been achieved. Within the set of hypotheses related to HAI assays CCI, the hypotheses testing will be performed in their associated strain, CCI. The hypotheses related to the secondary immunogenicity objective assessed using HAI assays CCI for each age stratum will be tested with same testing order CCI (CCI) after the secondary immunogenicity objective (HAI assays CCI) in the respective age stratum has been achieved.

CCI

A fixed-sequence testing procedure will be used to control the overall 1-sided type I error at CCI for all efficacy and immunogenicity hypotheses within each age stratum. The 1-sided alpha level of CCI will be used for each hypothesis that can be tested based on this strategy.

All vaccine efficacy estimations with any additional LCI cases collected after primary analysis will be descriptively summarized with a 95% CI. No type I error will be allocated to the remaining secondary endpoints or exploratory endpoints.

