5.3.2. Immunogenicity Data

Any assay results above the LLOQ are considered accurate, and their quantitated values will be reported. Antibody titers below the LLOQ, denoted as BLQ, or below the LOD will be set to **CCI** for GMT analysis. If the LLOQ is missing and the LOD is available for either serum or **CCI** data, the LOD will be used for LLOQ.

No other missing assay data will be imputed in the analyses. All immunogenicity analyses will be performed after the imputation of the antibody concentrations or antibody titers that are below the LLOQ.

When calculating a fold rise, the assay results will be converted to **CCI** if assay results are < LLOQ, except when the prevaccination assay result is < LLOQ while the postvaccination result is \geq LLOQ, in which case the prevaccination value will be set to the LLOQ. If both the numerator and denominator are < LLOQ, then both will be converted in the same way.

Values for sera that are insufficient (QNS), indeterminate results, or values recorded as “not done” will be set to “missing.” Additionally, any time point with no blood draws will not be included in the analysis. No imputation will be done for these missing values, as MCAR is assumed for immunogenicity data.

LLOQ results for each assay used in this study will be included in serology data transfer once they are available.

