6.2. Secondary Endpoint(s)

6.2.1. Immunogenicity Measured by HAI Titers

6.2.1.1. Main Analysis

The antibody titers measured by HAI assays [CCI](#) [CCI](#) will be analyzed separately. The analysis of antibody titers based on the HAI assay [CCI](#) [CCI](#) will have the following attributes. The analysis of the antibody titers based on the HAI assay [CCI](#) [CCI](#) will have the same attributes but will be based on the evaluable immunogenicity population (HAI assays [CCI](#) [CCI](#)).

- Estimand strategy: Hypothetical approach ([Section 2.2.3](#)).
- Analysis set: Evaluable immunogenicity population (HAI assays [CCI](#) [CCI](#)) ([Section 4](#)).
- Analysis methodology: Calculation of GMR and difference in seroconversion, as well as descriptive summary statistics ([Section 5.2.1](#) and [Section 5.2.2](#)).
- Analysis timing: Day 1, 4 weeks after study intervention.

- Intercurrent events and missing data: All data collected after or at intercurrent events will be excluded. Antibody titers data will be handled as described in [Section 5.3.2](#). Missing data will not be imputed.
- Reporting results:
 - GMRs for each strain in qIRV recipients compared to QIV recipients, and associated 2-sided 95% CIs, will be presented 4 weeks after study intervention, separately, for each age group (18 through 64 years of age, ≥ 65 years of age) in the northern hemisphere.
 - The difference in percentage of participants achieving seroconversion for each strain 4 weeks after vaccination in qIRV recipients compared to QIV recipients, and associated 2-sided 95% CIs, will be provided, separately, by age group (18 through 64 years of age, ≥ 65 years of age) in the northern hemisphere.
 - Descriptive statistics, including the sample size (n), GMTs, GMFRs, and 95% CI for the GMTs and GMFRs, will be presented, by study intervention ([Section 5.2.2](#)) and strain, separately, for each age group in the northern hemisphere and southern hemisphere, respectively.
 - The proportion of participants with HAI titers $\geq 1:40$ for each strain before vaccination and at each time point after vaccination, and the associated 2-sided Clopper-Pearson 95% CIs, will be provided, by study intervention, separately, for each age group (18 through 64 years of age, ≥ 65 years of age) in the northern hemisphere and southern hemisphere, respectively.

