6.2.1.2. Sensitivity/Supplementary Analysis

To support the assessment of immunogenicity estimands, as specified in [Section 2.2.2](#), the treatment policy strategy might be summarized with the mITT immunogenicity populations using the same presentation as specified in the main analysis.

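### The 4-week GMR noninferiority tests ignore the baseline HAI titer, although it will be measured alongside every 4-week titer; adjusting for it would narrow the intervals at almost no cost

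*SAP*

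**What the plan says.** SAP 5.2.2.3 defines the estimator: "The GMR will be calculated as the mean of the difference of logarithmically transformed assay results and exponentiating the mean". The interval follows: "Two-sided CIs will be obtained by calculating CIs using Student's t distribution for the mean difference of the logarithmically transformed assay results". Protocol 9.3.1.2.3 has the same definition. SAP 6.2.1.1 names no model beyond this ("Analysis methodology: Calculation of GMR and difference in seroconversion, as well as descriptive summary statistics"). SAP 6.2.1.2 adds only an optional repeat, in which "the treatment policy strategy might be summarized with the mITT immunogenicity populations".

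The GMR hypotheses belong to the fixed testing sequence in SAP 5.1.3. Each HAI family has eight hypotheses per age stratum: one GMR and one seroconversion difference for each of four strains. The first HAI family "will be tested after both primary efficacy objectives in the respective age stratum have been achieved", and the second follows only if the first succeeds. Under Protocol 9.3.3, noninferiority needs every GMR lower bound and every seroconversion lower bound to clear its margin.

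On baseline data, the footnotes to Protocol Table 6 state that the selected subsets "will be tested at Visit 1 and Visit 3 using HAIs". Every row of the table has testing at both visits, for both HAI types and both seasons. The evaluable immunogenicity sets in SAP 4 require a valid result only "at the 4-week postvaccination visit, and have no important protocol deviations"; no baseline result is required. SAP 5.3.2 gives one fixed replacement for titers below the LLOQ in GMT analysis. It has a different rule for fold rise when the baseline is below the LLOQ and the later result is not, "in which case the prevaccination value will be set to the LLOQ".

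**The concern.** Prevaccination HAI titer is the natural predictor of the 4-week titer for the same strain. It is collected in the participants being analysed and already enters the seroconversion half of the decision through the seroconversion definition. The GMR half leaves it out. If the two titers are correlated, the GMR intervals are wider than they need to be. Because all four GMR lower bounds must clear the margin, one wide interval can fail the objective for a stratum and stop testing of the second HAI family.

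Simply adding a baseline covariate would meet two difficulties. The analysis sets allow participants with no baseline result, and the plan has no rule for a missing covariate. Also, the fold-rise replacement for a baseline below the LLOQ depends on the postvaccination result, so it cannot serve as a baseline covariate.

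A smaller point is wording: the mean of a difference describes paired data and repeats the fold-rise text in SAP 5.2.2.2, whereas the two vaccine groups are independent.

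**Working it through.** **Inputs from the documents.** Unadjusted estimator and t interval (SAP 5.2.2.3, Protocol 9.3.1.2.3); paired Visit 1 and Visit 3 testing (Protocol 9.6.2 and Table 6); no baseline requirement (SAP 4); the below-LLOQ rules (SAP 5.3.2). The subset size, margin and alpha are redacted, and no log-titer SD is visible. There is therefore no power figure to reproduce, and none is claimed here.

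**Assumed inputs.** rho, the correlation between baseline and 4-week log titer; m, the share of evaluable participants with no baseline result, missing at random; and the share of baselines below the LLOQ. rho may differ by strain, assay and age stratum.

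**Step 1: complete baselines.** Linear adjustment targets the same log-scale difference and multiplies its variance by 1 − rho². Width factor = sqrt(1 − rho²).

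| rho | Width factor | Equivalent increase in sample size, 1/(1 − rho²) |
|---|---|---|
| 0.1 | sqrt(0.99) = 0.995 | 1.01 |
| 0.3 | sqrt(0.91) = 0.95 | 1.10 |
| 0.5 | sqrt(0.75) = 0.87 | 1.33 |
| 0.7 | sqrt(0.51) = 0.71 | 1.96 |

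**Step 2: missing baselines, m = 10%.** Filling the covariate with the pooled mean gives sqrt(1 − rho²(1 − m)). Dropping the participants gives sqrt((1 − rho²)/(1 − m)).

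| rho | Fill | Drop |
|---|---|---|
| 0.3 | sqrt(0.919) = 0.96 | sqrt(0.91/0.90) = 1.006 |
| 0.5 | sqrt(0.775) = 0.88 | sqrt(0.75/0.90) = 0.91 |
| 0.7 | sqrt(0.559) = 0.75 | sqrt(0.51/0.90) = 0.75 |

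Dropping helps only if 1 − rho² < 1 − m, that is, rho > sqrt(m): 0.22 at 5% missing and 0.32 at 10%. Filling never loses precision in this large-sample formula.

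**Step 3: simulation check.** With 400 per group (assumed), 2,000 runs and baselines missing at random, the simulated factors match the formulas:
- rho 0.3, m 10%: fill 0.959, drop 1.006
- rho 0.5, m 10%: fill 0.881, drop 0.914
- rho 0.5, m 5%: fill 0.874, drop 0.889

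A separate simulation with 300 per group and 4,000 runs, using pooled-mean fill plus a missing-baseline indicator, gave coverage of the 95% interval between 94.1% and 95.3% for the unadjusted, fill and drop analyses when baselines were missing.

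**Step 4: baselines below the LLOQ.** Replacing them with one constant below the LLOQ weakens the covariate. With 60% below the LLOQ (assumed), an underlying rho of 0.5 acts like 0.43, so the factor is 0.90 instead of 0.87. With 30% below, rho 0.5 acts like 0.48 and the factor is 0.88.

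**The case against.** The strongest reply is that nothing is broken. The unadjusted test is prespecified, unbiased and valid. rho, the missing share and the below-LLOQ share are all assumed, and with subset size, margin and alpha redacted nobody can show that the trial needs the extra precision. At rho 0.3 the interval narrows by only about 5%. The effect on the decision is diluted further: testing starts only after both efficacy noninferiority and efficacy superiority, and the four seroconversion tests gain nothing. The missing-baseline and below-LLOQ questions arise only if the covariate is adopted; in the plan as written, each below-LLOQ rule has its own stated use and the two do not conflict. The wording point is cosmetic, since the surrounding text makes clear that the groups are compared with each other.

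Most of this stands as a limit on the size of the gain. It does not remove the case for the change, which keeps the same log-scale target and uses data already planned. The missing-baseline and below-LLOQ rules are conditions for doing the adjustment properly, not faults in the current analysis. The optional pooled analysis across hemispheres (SAP 6.2.1.1) and the subset analyses (SAP 6.4) name no baseline adjustment either. The exploratory sections are redacted and cannot be checked.

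**Conclusion.** The point holds, as one of efficiency. The GMR tests under type I error control are unadjusted, and a same-strain baseline is planned wherever a 4-week titer is tested. Over assumed rho from 0.3 to 0.7 the interval narrows by 5% to 29% with complete baselines, and by 4% to 25% with 10% missing and pooled-mean fill. Near rho 0.1 the gain is negligible. The figures assume baselines missing at random and an approximately linear relation of log titers. Only the four GMR tests per HAI family and stratum benefit, so the gain for the all-strain decision is smaller than these single-test figures suggest. The change should be made, but the plan's validity does not depend on it.

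**What to change.** Before unblinding, amend SAP 5.2.2.3 and 6.2.1.1 as follows:

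- For each strain, HAI family and age stratum, fit a linear model of log 4-week titer on vaccine group and log baseline titer for that strain. Base the GMR noninferiority decision on the exponentiated adjusted group difference and its 95% CI. Report the unadjusted ratio of GMTs as supportive.
- Keep evaluable participants without a baseline result. Fill the covariate with the pooled mean log baseline for that strain, HAI family and stratum, computed blind to vaccine group. State that this fills a covariate only; missing 4-week titers remain unimputed.
- For baselines below the LLOQ, use the single fixed GMT-analysis value in SAP 5.3.2, not the fold-rise substitution.
- Describe the unadjusted log GMR as the difference between the group means of log titers.

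The cost is SAP text, a standard model and a slightly more complex decision analysis. SAP 2.1 lets the SAP modify the protocol's plan and requires an amendment only for major changes to primary endpoint definitions or their analyses. This endpoint is secondary, so SAP wording is enough, but Protocol 9.3.1.2.3 should be aligned so that the two documents do not differ on a test under type I error control. The choice must be fixed before results are seen; deciding on adjustment afterwards would undermine that control.

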5.2.2.4. Reverse Cumulative Distribution Curves

Empirical RCDCs will plot proportions of participants with values equal to or exceeding a specified assay value versus the indicated assay value, for all observed assay values. Data points will be joined by a step function, with the line first going down and then to the right to the next assay value.

5.2.3. Analyses for Efficacy Endpoints

Efficacy will be calculated for laboratory-confirmed influenza, caused by any influenza viral types/subtypes, associated with the occurrence of a protocol-defined ILI.

5.2.3.2. Comparing Person-Time Data

The RVE can also be estimated by comparing person-time data⁵ between study interventions. Two statistical methods (Poisson regression and Cox regression) are listed below.

5.2.3.2.1. Poisson Regression

The efficacy of qIRV relative to QIV (RVE) can also be estimated by:

$$RVE = 1 - IRR = 1 - \frac{CCI}{100}$$

where RVE is the efficacy of qIRV relative to QIV; IRR is the incidence rate ratio for qIRV to QIV. ^{CCI}

The incidence rate ratio IRR, CCI , and associated 95% CI, will be obtained using a scaled Poisson regression model. The offset will be the duration of follow-up in the influenza season for a given participant and the scale parameter will be estimated by the Pearson method, so the RVE and associated 95% CI can be estimated based on $\text{RVE} = 1 - \text{IRR}$.

Poisson regression with the study intervention as a covariate will be fit for each age group (18 through 64 years of age, ≥ 65 years of age), separately.

For participants with confirmed influenza (eg, first-episode LCI case with associated per-protocol ILI caused by any strain), their time of confirmed influenza will be used to calculate their person-time. For participants without confirmed influenza, CCI

will be used to calculate their person-time.

5.2.3.2.2. Cox Regression Model

The RVE can also be estimated by Cox regression, which utilizes the time to the first-episode of LCI cases.

$$RVE = 1 - \Theta_{qIRV}(t) / \Theta_{QIV}(t)$$

$$\equiv 1 - \Theta$$

where:

$\Theta_{qIRV}(t)$ = hazard rate (or force of illness in infectious diseases) in the qIRV group

$\Theta_{QIV}(t)$ = hazard rate in the QIV group

which can be further defined as $\Theta(t) = f(t)/S(t)$, for which $f(t)$ is the rate of first-occurrence confirmed influenza per unit time (t) and $S(t)$ is the survival function, ie, function of time without influenza events.

Cox regression requires the proportional hazard assumption, ie, hazard ratio $\Theta_{qIRV}(t)/\Theta_{QIV}(t)$ does not depend on t , but is constant Θ . This assumption is reasonable for a seasonal infectious disease.

A Cox regression model with the study intervention as a covariate will be fit for each age group (18 through 64 years of age, ≥ 65 years of age), separately.

For the time-to-event analysis, the time in the analysis will be the number of days from 14 days after vaccination to the first event for participants with confirmed influenza. Participants without confirmed influenza (eg, first-episode LCI case with associated per-protocol ILI, caused by any strain) will be censored at the end of the influenza season or at the data cutoff date for performing primary efficacy analysis, at the last successful contact, death, or discontinuation from the study. For these censored participants, the time for analysis will be calculated, in days, from 14 days after vaccination until censoring time.

In addition, a Cox regression model may be fit for each age group (18 through 64 years of age and ≥ 65 years of age) with the study intervention as a covariate, and the influenza season (northern hemisphere 2022-2023 and southern hemisphere 2023) as a stratification factor.

